8.7. Immune-Related Adverse Events

Immune-mediated AEs are AEs consistent with an immune-mediated mechanism or immune-mediated component for which non-inflammatory etiologies (*e.g.*, infection or tumor progression) have been ruled out. IMAEs can include events with an alternate etiology that were exacerbated by the induction of autoimmunity. Information supporting the assessment will be collected on the participant's case report form.

Every AE must be assessed by the Investigator with regard to whether it is considered immune mediated. For events which are potentially immune mediated, additional information will be collected on the participant's case report form.

AEs associated with nivolumab and ipilimumab exposure may represent an immunologic etiology. These irAEs may occur shortly after the first dose or several months after the last dose of nivolumab and/or ipilimumab treatment and may affect more than one body system simultaneously. Therefore, early recognition and initiation of treatment is critical to reduce complications. Based on existing clinical study data, most irAEs were reversible and could be managed with interruptions of nivolumab and/or ipilimumab, administration of corticosteroids and/or other supportive care. For suspected irAEs, ensure adequate evaluation to confirm etiology or exclude other causes. Additional procedures or tests such as bronchoscopy, endoscopy, skin biopsy may be included as part of the evaluation. Based on the severity of irAEs, withhold or permanently discontinue nivolumab and/or ipilimumab and administer corticosteroids. Dose modification and toxicity management guidelines for irAEs associated with nivolumab and/or ipilimumab are provided in [Appendix 8](#) and [Appendix 10](#).

8.8. Persistent or Recurrent Adverse Events

A persistent AE is one that extends continuously, without resolution, between subject evaluation time points. The initial severity of the event should be recorded, and the severity should be updated to reflect the most extreme severity any time the event worsens in intensity or grade.

When an AE becomes serious (regardless of changes in grade or severity), the eCRF should be updated to reflect this. As such, a new AE (serious event with onset date for when AE became serious) should be added to the eCRF.

However, the same does not hold true for AEs that change from serious to non-serious events. When an AE does not resolve but is downgraded from a serious to a non-serious event, a new AE is not required to be captured on the eCRF. A resolution date is required to be entered on the SAE form once an AE changes from a serious to non-serious event since this would result in the SAE resolving.

A recurrent AE is 1 that resolves between subject evaluation time points and subsequently recurs. Each recurrence of an AE should be recorded separately on the Adverse Event eCRF.

8.8.1. Abnormal Laboratory Values

Not every laboratory abnormality qualifies as an AE. A laboratory test result should be reported as an AE if it meets any of the following criteria:

- a. Accompanied by clinical symptoms.
- b. Results in a change in study treatment (*e.g.*, dosage modification, treatment interruption, or treatment discontinuation).
- c. Results in a medical intervention (*e.g.*, potassium supplementation for hypokalemia) or a change in concomitant therapy.
- d. Clinically significant in the Investigator's judgment.

It is the Investigator's responsibility to review all laboratory findings. Medical and scientific judgment should be exercised in deciding whether an isolated laboratory abnormality should be classified as an AE.

If a clinically significant laboratory abnormality is a sign of a disease or syndrome (*e.g.*, alkaline phosphatase and bilirubin 5 × ULN associated with cholecystitis), only the diagnosis (*i.e.*, cholecystitis) should be recorded on the Adverse Event eCRF.

If a clinically significant laboratory abnormality is not a sign of a disease or syndrome, the abnormality itself should be recorded on the Adverse Event eCRF, along with a descriptor indicating if the test result is above or below the normal range. Where possible, please enter a condition (e.g., neutropenia) rather than the lab finding (e.g., decreased neutrophils).

8.9. Classification of an Adverse Event (Seriousness, Severity, Causality, Expectedness)

It is important that the Investigator gives their own opinion regarding the **seriousness**, the **intensity** of the event, as well as the **cause-effect relationship** between an AE and the research or disease progression. This evaluation must be assessed by the Investigator and reported in the AE form. In addition, the Sponsor will be responsible for the evaluation of the **expectedness** of the event (see Section 8.10.3).

The seriousness should be evaluated according to international guidance (see definition Section 8.4, It is under Investigator's responsibility to evaluate the AE seriousness according to international guidance (see [ICH Topic E2A](#) and [EU DIRECTIVE 2001/20/EC of 4 April 2001](#) or further [regulation \(EU\) No 536/2014](#)). The Sponsor will review the AE seriousness. The seriousness may be upgraded (but never downgraded).

The severity of all AEs will be graded according to the NCI CTCAE version 5.0 on a 5-point scale (Grade 1 to 5):

- Grade 1: mild; asymptomatic or mild symptoms; clinical or diagnostic observations only; intervention not indicated.
- Grade 2: moderate; minimal, local or non-invasive intervention indicated; limiting age-appropriate instrumental activities of daily living (ADL)¹.
- Grade 3: severe or medically significant but not immediately life-threatening; hospitalization or prolongation of hospitalization indicated; disabling; limiting self-care ADL².
- Grade 4: life-threatening consequences; urgent intervention indicated.
- Grade 5: death related to AE.

The cause-effect relationship: The Investigator must make an assessment in the AE form whether the AE is related or not to the research, meaning:

- a procedure scheduled in the study protocol (e.g., exercise test, MRI), or
- a change or withdrawal of previous/concomitant treatment related to the conditions of the protocol.

Moreover, the Investigator has to assess if the AE is related to disease progression. Cases ticked “related” by the Investigator or judged by the Sponsor as having a reasonable suspected causal relationship to the IMP (AE linked to the mechanism of action of the IMP), will be considered as suspected adverse drug reactions. In general, if a relationship between AE and IMP is at least reasonably possible (i.e., the relationship cannot be ruled out) it is to be considered as “related”.

¹ Instrumental ADL refer to preparing meals, shopping for groceries or clothes, using the telephone, managing money, etc.

² Self-care ADL refer to bathing, dressing and undressing, feeding self, using the toilet, taking medications, and not bedridden”.

8.10. Reporting Procedures

[figure not shown]
8.10.1. Time Frame for AE Reporting

Any event meeting the above-mentioned definitions (see Section 8.3; [Figure \(8.10.1\) 1](#)) must be reported to the Sponsor on an AE form if it occurs:

- Before the first administration of IMP, for fatal events and events related to the research.
- At any time after the first administration of IMP.
- Up to 30 calendar days after the subject's last administration for all AEs and AESIs (including overdose).
- Up to 90 calendar days after the subject's last administration for all SAEs, or until the subject initiates new anti-cancer therapy, whichever is earlier.
- Up to 180 calendar days after the subject's last administration for all pregnancies and exposures during breastfeeding, or until the subject initiates new anti-cancer therapy, whichever is earlier.
- Irrespective of the time of onset in case of SAEs assessed as related to the research.

Of note, non-fatal events occurring between the signature of the ICF and the first administration of the IMP for which the Investigator does not consider an association with the research must be reported as medical history or as signs or symptoms related to the studied disease in the dedicated form of the eCRF.

Fatal events, related or not to the research, occurring after ICF signature and before first IMP administration, must be reported on the AE form.

Figure (8.10.1) 1 - Rules for Adverse Event Reporting

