Active treatment period: The planned duration of treatment is until disease progression. Subjects may be discontinued from treatment earlier due to unacceptable toxicity or other discontinuation criteria are met. End of Treatment (EOT) evaluations will be performed at the time of decision to discontinue treatment (or as close to the decision day as possible). Subjects may continue to receive up to a maximum of 24 months of nivolumab. Subjects who are still deriving clinical benefit after 24 months may continue to receive ivosidenib monotherapy until disease progression, unacceptable toxicity, or other discontinuation criteria are met.

Safety Follow-up period: Following discontinuation from study treatment, all subjects will have a 30-day Safety Follow-up visit. During the 30 (+5)-day Safety Follow-up period, all AEs and new medications (including new anti-cancer therapy) will be reported. Following the 30 (+5)-day Safety Follow-up period, subjects will be followed for safety for an additional 100 (+5) days after their last dose of immunotherapy or until they begin any other anti-cancer therapy, whichever is earlier.

Overall Survival (OS) Follow-up period: Subjects will be followed for OS. Subjects will be contacted every 12 weeks (\pm 2 weeks) beginning at the EOT visit for up to 2 years after the last subject has been enrolled, or until death, lost to follow-up, withdrawal of consent from overall study participation, or Sponsor ending study, whichever occurs first.

Data Review Team: A DRT composed of Sponsor medical, safety, and statistical representatives and study Investigator(s) will review the available safety data in all subjects enrolled in the 500 mg QD dose cohort of the Safety Lead-in phase in order to determine whether 500 mg QD is the ivosidenib RCD or whether the 250 mg QD dose level will be tested. If the 250 mg QD dose cohort is opened, the DRT will review the safety data in order to determine whether 250 mg QD is the RCD for the Expansion phase.

Contractual signatories

I, the undersigned, have read the foregoing protocol and the “Participant information and consent form” document attached to the protocol and agree to conduct the study in compliance with such documents, Good Clinical Practice and the applicable regulatory requirements.

INVESTIGATOR

NAME	
CENTER NUMBER	
DATE	
SIGNATURE	

**VICE PRESIDENT, CLINICAL DEVELOPMENT
HEAD OF CANCER METABOLISM GLOBAL DEVELOPMENT**

NAME	PPD
DATE	06 May 2024
SIGNATURE	PPD

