4.1.1.5. Post-Withdrawal Follow-up and End of Study

Safety Follow-up: Following discontinuation of study treatment, a post-treatment Safety Follow-up visit is to occur 30 (+5) days after the last dose of ivosidenib and immunotherapy. Subjects will be followed for an additional 100 (+5) days after the last dose of immunotherapy, unless they have started another anti-cancer therapy, whichever occurs earlier. Every effort must be made to perform protocol-specified evaluations unless consent to participate in the study is withdrawn.

PFS and Overall Survival Follow-up: Subjects who discontinue study treatment for reasons other than disease progression or withdrawal of consent from treatment and are alive by EOT will enter PFS follow-up with the same schedule of assessments as before study treatment discontinuation, until documented disease progression, death, the start of subsequent anti-cancer therapy, withdrawal of consent, or the end of study/study termination. Following discontinuation of study treatment, all subjects will be followed for survival. Subjects will be contacted every 12 weeks (\pm 2 weeks) after the subject experiences documented disease progression or begins subsequent anti-cancer therapy. This contact will continue for up to 2 years after the last subject has been enrolled, or until end of study, withdrawn consent, or are lost to follow-up, or the Sponsor has terminated the study, whichever occurs first.

Each subject will have an End of Study visit defined as the time at which the subject has permanently discontinued treatment and has completed the Safety Follow-up visit and survival follow-up period, or has died, been lost to follow-up, or withdrawn consent from the study or the Sponsor has terminated the study, whichever occurs first.

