23. Blood samples for exploratory biomarker assessments, including plasma circulating tumor DNA, will be collected at Screening and Day 1 of every cycle through Cycle 6, followed by every 6 months thereafter, and at EOT.
24. From the time of informed consent signing through the first dose of IMP, SAEs resulting from a study-related procedure and assessed as related to that procedure, as well as all fatal AEs whether or not related to research procedures, must be recorded. All AEs will be recorded from all subjects from the date of first dose through 30 days following the last dose of ivosidenib and/or nivolumab or ipilimumab, whichever occurs later. Following the 30-day Safety Follow-up period, any SAEs that occur within 100 days after last dose of immunotherapy are to be reported, or until the subject initiates another anti-cancer therapy, whichever is earlier. Only SAEs that are considered as related to either IMP by the Investigator are to be reported after the respective Safety Follow-up periods. Fatal events, related or not to the research, occurring after ICF signature and before first IMP administration, must be reported on an AE form.
25. All concomitant medications/procedures within 21 days of the first dose of IMP through 30 days (+ 5 days) after the last dose of ivosidenib and/or immunotherapy and through 100 days after the last dose of immunotherapy (whichever is later) are to be reported on the eCRF.
26. Subjects will be contacted every 12 weeks (\pm 2 weeks) after the subject experiences documented disease progression or begins subsequent anti-cancer therapy for up to 2 years after the last subject has been enrolled, or until death, lost to follow-up, withdrawal of consent from overall study participation, or Sponsor ending study, whichever occurs first.

Table (4.1.2) 2 - Pharmacokinetic and Pharmacodynamic Sampling for Subjects in the Safety Lead-in Phase: Ivosidenib in Combination with Nivolumab and Ipilimumab

Visit/Cycle:	Screening	Cycle 1 (21 Days)		Cycle 2 (21 Days)	Cycle 3 (21 Days)	Cycle 4 (21 Days Each Cycle)	Cycle 5 and Beyond (28 Days Each Cycle)
Study Day:	D-28 to D-1	D1	D15 (± 2 Days)	D1 (± 2 Days)	D1 (± 2 Days)	D1 (± 2 Days)	D1 (± 2 Days)
Blood Sample for Ivosidenib PK Pre-dose ^{1,2,3}		X	X	X	X	X	X ³
Blood Sample for PD (2-HG) Pre-dose ^{1,2,3}		X	X	X	X	X	X ³
Blood Sample for Nivolumab PK and Nivolumab ADA Pre-dose ^{1,2,4}		X		X	X	X	X ⁴
Blood Sample for Ipilimumab PK and Ipilimumab ADA Pre-dose ^{1,2,5}		X		X	X	X	

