8.10.3. Responsibilities of the Sponsor

In accordance with international guidance, the assessment of the seriousness and the causality of AEs is usually made by the Investigator but falls also under Sponsor's duties, who is responsible for ensuring that all suspected unexpected serious adverse reactions are reported to Competent Authorities and Ethics Committees.

The Sponsor will review the seriousness of the AEs and the causality of (at least) the SAEs, whether reported by the Investigator or upgraded by the Sponsor. The causality and the seriousness may be upgraded (but never downgraded). Anonymized copies of documents providing useful information such as reports of further consultations, laboratory test reports, and reports of other examinations aiding diagnosis may be requested for the event assessment. If the assessments of the Investigator and the Sponsor are different, both will be reported in the clinical study report (CSR).

In addition, the Sponsor is responsible for determining whether an AE is **expected or unexpected**. An AE will be considered unexpected if the nature, severity, or frequency of the event is not consistent with the risk information previously described for the IMP.

Independently of the regulatory obligations of the Investigator, the Sponsor must report the pharmacovigilance data and any new safety finding likely to affect the benefit/risk balance of the product, required in ICH GCP guidelines and local regulations, to the appropriate Authorities, to all the Investigators involved, and to the trial participants involved (through the Investigators) as described in Section 13.4. **Responsibilities of Data Review Committee**

During the Safety Lead-in phase, the DRT, composed of Investigator(s) and the Sponsor's medical, safety, and statistical representative(s), will meet to evaluate clinical and laboratory safety data in order to make decisions regarding determination of the RCD. The DRT will meet at minimum:

- Before deciding that a dose is the RCD and the Expansion phase can be opened.
- If the rate of DLTs indicates that the dose should be de-escalated, the DRT will meet to determine if the 250 mg QD dose should be tested.
- If either the 500 mg and/or the 250 mg dose is determined to have unacceptable toxicity.

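### Protocol Section 8.10.1 and schedule footnote 24 set different end dates for collecting SAEs regardless of causality: 90 days from an unnamed last dose against 100 days from the last immunotherapy dose

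*Protocol*

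**What the plan says.** Five places in the protocol bear on how long SAEs are collected after treatment.

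- **Section 8.10.1 (Time Frame for AE Reporting):** "Up to 90 calendar days after the subject's last administration for all SAEs", ending early if new anti-cancer therapy starts. The bullet does not say which drug's last administration starts the clock. A later bullet removes the time limit for related events: "Irrespective of the time of onset in case of SAEs assessed as related to the research".
- **Footnote 24 to Table (4.1.2) 1, repeated in the GBR table of Appendix 13:** all AEs are recorded "through 30 days following the last dose of ivosidenib and/or nivolumab or ipilimumab, whichever occurs later". After that, "any SAEs that occur within 100 days after last dose of immunotherapy are to be reported", again ending early if another anti-cancer therapy starts. SAEs the Investigator considers related remain reportable afterwards.
- **Synopsis, safety follow-up period:** "subjects will be followed for safety for an additional 100 (+5) days after their last dose of immunotherapy".
- **Section 4.1.1.5:** "Subjects will be followed for an additional 100 (+5) days after the last dose of immunotherapy".
- **Section 8.10.3:** the Sponsor reviews seriousness for AEs and causality for at least the SAEs, and may raise either but not lower it.

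On the analysis side, protocol Section 10.1.6.2 and SAP Sections 4.2 and 5.4.1.2 use 30 days after the last study drug in general, and 100 days after the last nivolumab dose for immune-mediated events.

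**The concern.** Two current passages give sites different instructions on the same data item, and nothing in the text ranks one above the other. The synopsis and Section 4.1.1.5 agree with footnote 24 on 100 days, which leaves Section 8.10.1 as the outlier on length. It is also the section a site would naturally consult for reporting rules.

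SAEs are part of the primary endpoint of the Safety Lead-in phase, in what Section 2.5 describes as the first study of this triple combination. Section 8.7 warns that immune-related events can appear months after the last antibody dose. Because related SAEs have no time limit, the conflict falls on events the Investigator has called unrelated. Those are the events for which the Sponsor's second look at causality matters most, and the Sponsor cannot review an event that was never sent in.

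**Working it through.** This is a comparison of texts with a day count. The plan has no power, alpha or sample-size figure to reproduce here.

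**Inputs**
- 90 days after the last administration (Section 8.10.1).
- 100 days after the last immunotherapy dose, and 30 days after the last dose of any study drug for all AEs (footnote 24).
- Ivosidenib may outlast the antibodies: after 24 months of nivolumab, or when one drug is dropped from Cycle 5 onward (Section 4.1.1.3), or when both antibodies are stopped (Section 8.12.2).

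**Set-up.** Count days from the last immunotherapy dose. Let g be the number of days from that dose to the last dose of any study drug. Assume for now that Section 8.10.1 counts from the last dose of any study drug, and that no new anti-cancer therapy starts.

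- Section 8.10.1 closes on day g + 90.
- Footnote 24 closes on day max(100, g + 30).
- Difference (Section 8.10.1 minus footnote 24) = min(g − 10, 60).

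| g | Section 8.10.1 | Footnote 24 | Difference |
|---|---|---|---|
| 0 | 90 | 100 | −10 |
| 10 | 100 | 100 | 0 |
| 28 | 118 | 100 | +18 |
| 70 | 160 | 100 | +60 |
| 180 | 270 | 210 | +60 |

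**Example in study days.** Last nivolumab on Day 85 and last ivosidenib on Day 200, so g = 200 − 85 = 115.
- Section 8.10.1: 200 + 90 = Day 290.
- Footnote 24: the later of 85 + 100 = Day 185 and 200 + 30 = Day 230, so Day 230.
- Difference: 290 − 230 = 60 days.

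**Other reading of the anchor.** If the last administration in Section 8.10.1 means the last immunotherapy dose, its SAE limit falls at day 90, ten days short of the 100-day rule, and it is never the longer window.

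**Which events differ.** Related SAEs are reportable without limit under both rules. New anti-cancer therapy closes both windows on the same day if it starts before either limit. What remains is SAEs judged unrelated, falling between the two closing dates, in participants still under follow-up and not on new therapy.

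**Reach into the analysis.** SAP Section 5.4 restricts summaries to the on-treatment period. A non-immune SAE more than 30 days after the last study drug enters no summary table under either rule. An immune-mediated SAE on Days 91 to 100 after the last nivolumab dose would count under SAP Section 5.4.1.2, but could go uncollected only if the site followed Section 8.10.1 and also judged it unrelated. DLT assessment covers the first 42 days of dosing and is untouched.

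**The case against.** The strongest reply is that little in the reported results depends on this. It is largely right: related SAEs are safe under both rules, and the summaries stop at 30 days except for immune-mediated events. Section 8.7 treats an event as immune-mediated only when non-inflammatory causes are excluded, so one that is also judged unrelated to the antibodies should be uncommon. The SAP reports that enrolment stopped at 7 participants and that the termination letter was dated 21 August 2024.

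The 60-day figure also depends on reading the last administration as that of any study drug. That is the natural reading but not a stated one. Figure (8.10.1) 1 is not available in the text reviewed and might settle it.

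Several stronger readings are tempting, and the documents do not support them.

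- *Every participant is affected.* No. The windows coincide at g = 10, and early new therapy, death, loss to follow-up or withdrawal of consent removes the difference.
- *The synopsis and Section 4.1.1.5 set a rival SAE window.* No. They set the length of safety follow-up and do not name SAEs; only footnote 24 states the 100-day SAE rule.
- *Footnote 24 stops collection while ivosidenib continues.* No. It keeps all AEs open until 30 days after the last dose of any drug; it is shorter only relative to Section 8.10.1.
- *Ascertainment did differ between sites.* The text makes this possible, but nothing shows that sites followed different pages.

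None of this removes the contradiction. Both passages are current text, and the shared new-therapy cut-off does not reconcile them. With 7 participants, a single missing SAE is also a visible part of the record.

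**Conclusion.** The inconsistency is real and concerns both the length of the window and the dose it counts from. When all drugs stop together, ten days (Days 91 to 100) are covered by footnote 24 only, although the plan's own immune-mediated period runs to 100 days after the last nivolumab dose. When ivosidenib continues alone, Section 8.10.1 is the longer window by up to 60 days, provided it counts from the last dose of any study drug.

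The consequence is limited to the collection and listing of SAEs judged unrelated in participants who have not started new anti-cancer therapy. A reader might infer that the SAP's immune-mediated analysis loses events in any quantity. The documents do not support that, since the loss needs an event that is immune-mediated, serious, late and judged unrelated. The point should be corrected because SAEs belong to a primary endpoint and the repair is simple.

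**What to change.** State one SAE window and use the same words in Section 8.10.1 and its figure, footnote 24 in the main and GBR tables, Section 4.1.1.5 and the synopsis. The wording should:

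- collect SAEs regardless of causality at least to 100 days after the last nivolumab or ipilimumab dose;
- name one explicit period after the last ivosidenib dose, with the Sponsor choosing between the 30 and 90 days its own passages imply, and take the later of the two end dates;
- name the drug for each limit;
- keep the cut-off at new anti-cancer therapy and the open-ended rule for related SAEs.

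**Cost.** Text edits in those places and in the eCRF completion guide. Relative to Section 8.10.1, ten more days of SAE reporting when all drugs stop together, ending at the 100-day visit already planned. Relative to footnote 24, up to 60 more days if the longer ivosidenib period is chosen. No safety visit is scheduled in that stretch: the 100-day visit counts from the last nivolumab dose, which is Day 185 in the example. The Sponsor would need to say how those reports are to be obtained.
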